### 9.4.1 Efficacy Analyses

The analysis of the primary efficacy endpoint family will compare the 2 treatment groups (OP0201, placebo) with respect to the proportion of Participants with no bulging of the TM at the Day 4 Visit as well as the proportion of Participants with no MEE at the Day 12 Visit using the ITT population for which Participants with missing data at the Day 4 Visit will be considered as having bulging TM and those with missing data at the Day 12 Visit will be considered as having MEE. A sensitivity analysis will be done that defines the endpoints as no bulging of the TM at the Day 4 Visit and no recurrence of bulging TM throughout the remainder of the study, and no MEE at the Day 12 Visit and no recurrence of MEE throughout the remainder of the study. Sensitivity analyses will also be done using the per-protocol population. Treatment groups will be statistically compared using generalized estimating equations (GEE), if possible, with an alternative method (eg, logistic regression) at each visit as an alternative if GEE convergence cannot be achieved. Randomization stratifiers (daycare attendance [yes, no] and age group [ $\geq 6$  to  $<12$  months,  $\geq 12$  to  $\leq 24$  months]) and degree of TM bulging at baseline will be covariates. Tympanic membrane bulging at baseline will also be evaluated as a potential effect modifier.

The step-up Hochberg procedure will be used to control the familywise Type 1 error. Specifically, the endpoint with the highest p-value will be tested first at the 0.05 significance

level and, if significant, both endpoints will be declared significant; if the endpoint with the highest p-value is not significant at the 0.05 level, the other endpoint will be tested at the 0.025 significance level. A positive treatment effect on efficacy will be concluded if at least 1 of the 2 endpoints in the primary efficacy endpoint family is significant

Descriptive statistics will be provided for the primary efficacy endpoint family by the following sub-groups: age stratum ( $\geq 6$  to  $< 12$  months,  $\geq 12$  to  $\leq 24$  months), race (Caucasian, non-Caucasian), gender (male, female), laterality of disease (unilateral, bilateral), history of recurrent AOM defined as 3 or more episodes in the preceding 6 months or 4 or more episodes over the course of 12 months (yes, no), and daycare attendance stratum defined as exposure to 3 or more children outside of the home for 10 or more hours per week (yes, no).

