12.1 Bulging TM

The presence/absence of bulging TM will be evaluated as part of the ear examination (see Section 11.4) done at each study visit; each ear will be evaluated separately.

A listing of bulging TM will be produced separately from the listing of ear examination parameters noted in Section 11.4.

Endpoints

The definition of bulging TM will be presence of 1+, 2+, or 3+ bulging on ear examination. Note: at least mild bulging is an inclusion criterion.

No bulging TM at the Day 4 visit is one of two endpoints in the primary efficacy endpoint family (see Section 13.5). The hypothesis set to be tested is:

Confidential Page 22 of 35

$$\begin{aligned} &H_o \colon P_A = P_P \\ &vs. \\ &H_A \colon P_A \neq P_P \end{aligned}$$

where P_A and P_P are the population proportions for OP0201 and placebo, respectively, for no bulging TM 4 days after the start of a 10-day treatment regimen.

The following sensitivity analyses will be done:

- PP analysis population
- Complete case (ie, mITT subjects who completed the Day 4 visit; see Section 13.3)
- Complete case with the endpoint defined as no bulging TM at the Day 4 visit and no recurrence of bulging TM (see Section 12.7) throughout the remainder of the study, assessed at the Day 28 visit. In this instance, "complete case" is equivalent to mITT subjects who completed the Day 28 visit.

No bulging TM assessed at the Day 12 and Day 28 visits are secondary endpoints.

Summaries and Analyses (see Section 13)

No bulging TM will be summarized and analyzed separately by visit using logistic regression. Summary tables will include frequencies and percentages of no bulging TM for each treatment group by visit and p-values for the differences. Crude rates of no bulging TM by treatment group and visit will be graphically displayed using bar charts.

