12.2 MEE

Otoscopy will be performed at each study visit (as well as 30 minutes post-dose on Day 1, for safety only) to evaluate the presence/absence of MEE; each ear will be evaluated separately, and a listing will show presence/absence of MEE for each ear separately.

Endpoints

No MEE at the Day 12 visit is one of two endpoints in the primary efficacy endpoint family (see Section 13.5). The following sensitivity analyses will be done:

- PP analysis population
- Complete case (ie, mITT subjects who completed the Day 12 visit; see Section 13.3)
- Complete case with the endpoint defined as no MEE at the Day 12 visit and no recurrence of MEE throughout the remainder of the study. In this instance, "complete case" is equivalent to mITT subjects who completed the Day 28 visit.

The hypothesis set to be tested is:

 H_o : $P_A = P_P$ vs. H_A : $P_A \neq P_P$

Confidential Page 23 of 35

where P_A and P_P are the population proportions for OP0201 and placebo, respectively, for no MEE 12 days after the start of a 10-day treatment regimen.

No MEE at the Day 4 and Day 28 visit are secondary endpoints.

Summaries and Analyses (see Section 13)

No MEE will be summarized and analyzed separately by visit using logistic regression. Summary tables will include frequencies and percentages of no MEE for each treatment group by visit and p-values for the differences. Crude rates of no MEE by treatment group and visit will be graphically displayed using bar charts.

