13.3 Missing Observations

For the primary efficacy analysis, multiple imputation will be used for missing observations with only treatment group included in the imputation model; ie, the observed within-treatment-group Bernoulli distribution of response will be the distribution from which random values are drawn to replace missing observations. The number of imputations will be the percentage of subjects with missing data, rounded up to an integer. Results from multiple imputations will be combined using the Rubin method.⁸ A complete-case sensitivity analysis will also be done, whereby for each endpoint only subjects with complete data are included. For secondary endpoints, only complete-case analyses will be done.

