APPENDIX B: TABLES OF CONTENTS FOR TABLES, FIGURES, AND LISTINGS

TABLES

NUMBER	TITLE	POPULATION
Study Popula	tion	
14.1.1	Subject Disposition	all randomized
14.1.2	Eligibility	all randomized
14.1.3	Reasons for Screen Failure	Screened excluding
		randomized
14.1.4	Protocol Deviations	all randomized
14.1.5	Analysis Populations	all randomized
14.1.6	Baseline Characteristics	all randomized
14.1.7.1	Medical History	all randomized
14.1.7.2	Baseline Symptoms	all randomized
14.1.8	Pre-Treatment Adverse Events	Screened
Treatments		
14.1.9.1	Study Treatment Exposure	Safety
14.1.9.2.1	Study Treatment Compliance	Safety
14.1.9.2.2	Oral Antibiotic Compliance	Safety
14.1.10.1	Prior Medications	all randomized
14.1.10.2	Concomitant Medications	Safety
Efficacy Endp	oints	
14.2.1.1	Bulging TM	mITT
14.2.1.2	Bulging TM	Per Protocol
14.2.1.3	Bulging TM	Complete Case
14.2.1.4	Bulging TM and No Recurrence	mITT
14.2.1.5	Bulging TM by age group	mITT
14.2.1.6	Bulging TM by sex	mITT
14.2.1.7	Bulging TM by race	mITT
14.2.1.8	Bulging TM by disease laterality	mITT
14.2.1.9	Bulging TM by history of recurrent AOM	mITT
14.2.1.10	Bulging TM by daycare attendance	mITT
14.2.1.11.1	Bulging TM by study site	mITT
14.2.2.1	MEE	mITT
14.2.2.2	MEE	Per Protocol
14.2.2.3	MEE	Complete Case
14.2.2.4	MEE and No Recurrence	mITT
14.2.2.5	MEE by age group	mITT
14.2.2.6	MEE by sex	mITT
14.2.2.7	MEE by race	mITT
14.2.2.8	MEE by disease laterality	mITT
14.2.2.9	MEE by history of recurrent AOM	mITT
14.2.2.10	MEE by daycare attendance	mITT
14.2.2.11.1	MEE by study site	mITT
14.2.3.1	Tympanogram Shifts from Baseline	Tympanogram Subset
14.2.4.1	AOM-SOS Scale Score – 10-Day Mean	mITT
14.2.5.1.1	AOM Cure	mITT

Confidential Page 32 of 35

14.2.5.1.2	AOM Cure – Sensitivity Analysis	mITT
14.2.6.1	AOM-SOS Response	mITT
14.2.7.1	AOM Treatment Failure, AOM Relapse, AOM Recurrence	mITT
Safety Endp	oints	
14.3.1.1	Summary of TEAE Incidence	Safety
14.3.1.2.1	Incidence of TEAEs by System Organ Class (SOC) and Preferred Term (PT)	Safety
14.3.1.2.2	Incidence of TEAEs Related to Study Treatment by SOC and PT	Safety
14.3.1.2.3	Incidence of TEAEs by Severity, by SOC and PT	Safety
14.3.1.2.4	TEAEs by PT in Descending Order of Incidence	Safety
14.3.1.3.1	Incidence of TESAEs by SOC and PT	Safety
14.3.1.3.2	Incidence of TESAEs Related to Study Treatment by SOC and PT	Safety
14.3.1.3.3	TESAEs by PT in Descending Order of Incidence	Safety
14.3.1.4	Non-TEAEs	Safety
14.3.9.1	Vital Signs, Observed Values and Changes from Baseline	Safety

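### The sustained-response sensitivity analyses drop children already known to have failed if they leave before Day 28

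*SAP*

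**What the plan says.** SAP 12.1 lists this sensitivity analysis for the first primary endpoint: "Complete case with the endpoint defined as no bulging TM at the Day 4 visit and no recurrence of bulging TM" up to Day 28. SAP 12.2 does the same for the second: "Complete case with the endpoint defined as no MEE at the Day 12 visit and no recurrence of MEE throughout the remainder of the study". Both sections then say who is analysed. Complete case, for this purpose, "is equivalent to mITT subjects who completed the Day 28 visit".

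The general rule in SAP 13.3 is looser: "for each endpoint only subjects with complete data are included". Read alone, it could keep a child whose composite is already settled, but the specific Day 28 definition in 12.1 and 12.2 overrides it.

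Protocol 9.4.1 plans the same analysis, with the first endpoint defined as "no bulging of the TM at the Day 4 Visit and no recurrence of bulging TM throughout the remainder of the study", and states no restriction to completers. Its missing-as-failure rule is written for the Day 4 and Day 12 visits.

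SAP 16 reports the move from ITT to mITT, the replacement of missing-as-failure by multiple imputation, and an added complete-case analysis. It does not mention the Day 28 denominator. In SAP Appendix B, Table 14.2.1.4 ("Bulging TM and No Recurrence") and its MEE counterpart 14.2.2.4 carry the population label mITT, while Tables 14.2.1.3 and 14.2.2.3 are labelled Complete Case.

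**The concern.** The endpoint has two parts joined by *and*: clear at the index visit, and still clear afterwards. Failing the first part settles the result, and nothing seen at Day 28 can change it. Requiring a Day 28 visit therefore removes children whose outcome is known, along with those whose outcome is not.

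Completion to Day 28 comes after the index-visit result and may depend on it. If it does, the completers are a selected group in each arm and the sustained-response rates shift. If the selection differs between arms, the treatment difference shifts too.

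The SAP handles the parallel case differently. In 12.6 and 12.7, an early leaver is excluded from the relapse or recurrence analysis only if no qualifying AOM visit was seen, and a leaver with an observed event stays in. SAP 12.1 refers to 12.7 for recurrence but does not carry that principle into its own denominator.

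**Working it through.** **Inputs.** SAP 5 gives planning rates for placebo of 0.40 (no bulging, Day 4) and 0.30 (no MEE, Day 12), a difference of 0.25, 70 children per arm and 10% dropout. The OP0201 rates are therefore 0.65 and 0.55. The Protocol assumes 12% dropout. Neither document gives dropout by response status or a recurrence rate, so those below are assumptions.

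**The plan's own figure.** The documents state no power or sample size for the sustained analyses. As a check on the planning rates, take 70 × 0.9 = 63 evaluable per arm and independent endpoints. Single-endpoint power is 0.721 and 0.731 at two-sided 0.025, and 0.810 and 0.818 at 0.05. Hochberg power for at least one endpoint is 1 − (0.279)(0.269) + (0.089)(0.087) = 0.933, which matches the SAP's 93%.

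**How many children are removed.** Suppose 10% leave between the index visit and Day 28, whatever their response. The settled failures deleted are then:

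- Bulging: 70 × 0.60 × 0.10 = 4.2 on placebo and 70 × 0.35 × 0.10 = 2.45 on OP0201.
- MEE: 70 × 0.70 × 0.10 = 4.9 and 70 × 0.45 × 0.10 = 3.15.

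If every leaver were a failure, 7 per arm would go. (The mITT set is three children smaller in total, which hardly matters here.)

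**What the completer analysis estimates.** Let s and f be the success and failure shares at the index visit, and ds and df the proportions of each who leave. With no later recurrence:

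completer rate = s(1 − ds) / [s(1 − ds) + f(1 − df)]

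With ds = 0.05 in both arms and a true difference of 0.25:

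| Endpoint | df placebo / OP0201 | Placebo | OP0201 | Difference | Mean dropout |
|---|---|---|---|---|---|
| Bulging | 0.15 / 0.15 | 0.38/0.89 = 0.427 | 0.6175/0.915 = 0.675 | 0.248 | 9.75% |
| Bulging | 0.25 / 0.10 | 0.38/0.83 = 0.458 | 0.6175/0.9325 = 0.662 | 0.204 | 11.9% |
| Bulging | 0.10 / 0.25 | 0.38/0.92 = 0.413 | 0.6175/0.88 = 0.702 | 0.289 | 10.0% |
| MEE | 0.25 / 0.10 | 0.285/0.81 = 0.352 | 0.5225/0.9275 = 0.563 | 0.211 | 13.1% |

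The MEE row needs 19% loss on placebo and 7.25% on OP0201 after Day 12 alone, which is above the planned 10–12% total.

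**Dropout fixed at 10% per arm.**

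- Unrelated to response: the difference stays 0.25 for both endpoints.
- All leavers are failures in both arms: bulging 0.40/0.90 = 0.444 against 0.65/0.90 = 0.722, difference 0.278. Equal total dropout here still means unequal loss among failures: 0.10/0.60 = 17% against 0.10/0.35 = 29%.
- All leavers are failures on placebo only: 0.206 (bulging), 0.217 (MEE). On OP0201 only: 0.322 and 0.311.
- With an assumed 20% later recurrence, the bulging difference runs from 0.164 to 0.258 against a true 0.20.

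**Direction.** If well children skip Day 28 more often (15% of successes, 5% of failures), the placebo rate is 0.34/0.91 = 0.374, below the true 0.40.

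**A partial repair is not enough.** Restoring settled failures while still dropping responders who leave pushes rates down. With 10% random dropout, placebo bulging becomes 0.36/(0.36 + 0.60) = 0.375 instead of 0.40.

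**The case against.** The strongest reply is that little depends on this. The study is an exploratory Phase 2a, these analyses sit outside the Hochberg decision, and the primary and index-visit complete-case analyses still count these children as failures. If dropout is unrelated to response, the difference is unbiased. All of that stands and limits the weight of the point. It does not explain why a settled failure should be discarded.

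A reader might also infer more than the documents support:

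- *That sustained response is overstated.* This holds only if failures leave more often than successes, and the documents do not say so. Treatment failure leads to further antibiotic therapy (Protocol 4.1 and 6.1.4) and is not itself an exit criterion in Protocol 7.2.
- *That this is the only look at durability.* No bulging at Days 12 and 28, no MEE at Day 28, AOM relapse and AOM recurrence are all planned endpoints.
- *That the SAP overturned a Protocol rule of missing-as-failure through Day 28.* Protocol 9.4.1 gives no rule for missing Day 28 data. The supported statement is that the Protocol has no completer restriction.
- *That the change is undisclosed, or that Appendix B contradicts the text.* SAP 16 discloses the shift to complete-case analysis, though not this denominator. The SAP also labels its complete-case secondary tables mITT, so that label is uneven rather than a contradiction.
- *That deletion is certain for every early leaver.* Day 28 measurements are due at early exit, and it is unclear whether such an examination counts as completing the visit. SAP 8.7 excludes observations outside Study Days 26–30, which points to exclusion, so the early-exit examination does not clearly rescue these children.

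**Conclusion.** The point holds for both endpoints, and only for the sustained-response sensitivity analyses. As written, they discard settled outcomes: roughly 2 to 5 children per arm at 10% dropout unrelated to response, and up to 7 if all leavers are failures. The effect on the difference runs from nothing, when leaving is unrelated to response, to several points when it depends on response differently by arm. In the bulging illustrations the difference is 20.4 to 28.9 points against 25. The extreme cases at 10% dropout per arm give 20.6 to 32.2.

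These figures rest on the planning rates, no later recurrence except where stated, and assumed dropout by response. They show possible size, not an expected bias, and the sign cannot be known from the documents. The change is worth making because it is cheap and removes an avoidable selection. No conclusion about trial success depends on it.

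**What to change.** 1. Run both sustained analyses on all mITT children.
2. Score as a failure any child with bulging at Day 4 (MEE at Day 12) or at any later examination, including an early-exit one, whether or not Day 28 was completed. This needs a stated exception to the SAP 8.7 windows. In 12.1, which ties recurrence of bulging to the Day 28 visit, it also needs wording that any later examination counts.
3. Treat as missing only children with no observed failure and incomplete follow-up. Multiply impute them from same-arm children who were also clear at the index visit, and do not drop them. In every no-recurrence illustration above, this returns 0.40 against 0.65 (or 0.30 against 0.55). It assumes that, among index-visit responders, leaving is unrelated to later recurrence.
4. A missing-as-failure version can be added as a further sensitivity analysis. It pulls the difference down: with 10% random dropout, bulging is 0.36 against 0.585, or 22.5 points.
5. List the change of denominator in SAP 16, and align the population labels of Tables 14.2.1.4 and 14.2.2.4 with the text.

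The cost is SAP wording and a small change to the derivation. No new data are needed.

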12.2 MEE

Otoscopy will be performed at each study visit (as well as 30 minutes post-dose on Day 1, for safety only) to evaluate the presence/absence of MEE; each ear will be evaluated separately, and a listing will show presence/absence of MEE for each ear separately.

Endpoints

No MEE at the Day 12 visit is one of two endpoints in the primary efficacy endpoint family (see Section 13.5). The following sensitivity analyses will be done:

- PP analysis population
- Complete case (ie, mITT subjects who completed the Day 12 visit; see Section 13.3)
- Complete case with the endpoint defined as no MEE at the Day 12 visit and no recurrence of MEE throughout the remainder of the study. In this instance, "complete case" is equivalent to mITT subjects who completed the Day 28 visit.

The hypothesis set to be tested is:

 H_o : $P_A = P_P$ vs. H_A : $P_A \neq P_P$

Confidential Page 23 of 35

where P_A and P_P are the population proportions for OP0201 and placebo, respectively, for no MEE 12 days after the start of a 10-day treatment regimen.

No MEE at the Day 4 and Day 28 visit are secondary endpoints.

Summaries and Analyses (see Section 13)

No MEE will be summarized and analyzed separately by visit using logistic regression. Summary tables will include frequencies and percentages of no MEE for each treatment group by visit and p-values for the differences. Crude rates of no MEE by treatment group and visit will be graphically displayed using bar charts.

12.3 Tympanogram

For a subset of the mITT population, tympanograms will be performed at each study visit to assess middle ear function. Each ear will be rated separately as Type A, Type B, or Type C.

Endpoints

Secondary endpoints based on tympanogram will be:

• Normal tympanogram (Type A) in either ear, assessed at the Day 4, 12, and 28 visits

A listing of tympanogram parameters will show peak height, gradient width, peak pressure, values derived, test results, ear canal volume value, predictive value, and rating.

Summaries and Analyses

Summary tables will include frequencies and percentages of shifts from baseline for each treatment group by visit. Crude rates of normal tympanogram by treatment group and visit will be graphically displayed using bar charts. There will be no statistical analysis of normal tympanogram.

12.4 AOM-SOS Scale

The AOM-SOS scale is scored by the parent/caregiver once daily at home and recorded in a diary over the 10-day duration of the antibiotic and study treatment period and also at in-clinic visits on Day 1, 4, 12 and 28. The scale consists of 5 questions rated on a 6-point scale, with lower scores associated with better symptom status: 0 = no, 1 = almost none, 2 = a little, 3 = some, 4 = a lot, 5 = an extreme amount. A total score for each day will be calculated in the AOM-SOS analysis data set (ie, not in the eCRF) as the sum of the 5 individual scores. Missing observations for individual questions will not be possible, which is a built-in feature of the data collection instrument; either all 5 questions will have responses or none of the 5 questions will have responses.

At the screening visit the parent/caregiver will be asked to score the AOM-SOS scale as part of the screening criteria for the study; a score of at least 5 is an inclusion criterion. This is the only baseline assessment of the AOM-SOS scale.

Confidential Page 24 of 35

Listings for AOM-SOS scale will show observed values at each time point collected for both diary and in-clinic, the 10-day mean from diary, and absolute and percent changes from baseline in the in-clinic AOM-SOS scores for Days 4, 12, and 28.

Endpoints

Secondary endpoints based on the AOM-SOS scale will be:

- 10-day mean AOM-SOS total score based on diary data, calculated for each subject as the mean total score over the 10-day treatment period. If the Day 4 assessment is missing from the diary, the Day 4 in-clinic assessment may be used but only if done on Study Day 4. If more than 10 days of AOM-SOS scores are available, only the first 10 days will be used to calculate the mean. If less than 10 days of AOM-SOS scores are available, 10-day mean score will not be calculated.
- Complete or near complete resolution of symptoms (AOM cure), defined as in-clinic AOM-SOS score < 2, assessed at the Day 4, 12, and 28 visits.
- AOM-SOS response, defined as at least a 50% reduction from baseline in the in-clinic AOM-SOS score, assessed at the Day 4, 12, and 28 visits.

Since a Day 4 assessment should be available from both the diary and the in-clinic visit, the in-clinic assessment will be used for the resolution and response endpoints. If the in-clinic assessment is not available, the Day 4 diary assessment will be used.

In a sensitivity analysis, AOM cure will be defined as AOM-SOS score = 0.

Summaries and Analyses (see Section 13)

The 10-day mean AOM-SOS total score will be analyzed using a general linear model (GLM) with baseline AOM-SOS total score included as a covariate. A summary table will include means and SDs for each treatment group and a p-value for the difference.

AOM cure and AOM-SOS response will be summarized and analyzed separately by visit using logistic regression with baseline AOM-SOS total score included as a covariate. Summary tables will include frequencies and percentages of AOM cure and AOM-SOS response for each treatment group by visit and p-values for the differences.

12.5 **AOM Treatment Failure**

AOM treatment failure (clinical failure) will be defined as:

- moderate to severe bulging of the TM, or
- mild bulging of the TM with
 - o recent (less than 48 hours) onset of ear pain (otalgia), or
 - o intense erythema of the TM

AOM treatment failure (clinical failure) will be available in the eCRF and will not be programmatically derived. As a cross-check, a listing will be provided that shows degree of bulging TM, otalgia, and erythema in each ear and AOM treatment failure status at Day 12.

Confidential Page 25 of 35

Endpoints

AOM treatment failure (clinical failure) at the Day 12 visit will be a secondary endpoint.

Summaries and Analyses (see Section 13)

AOM treatment failure (clinical failure) will be analyzed using logistic regression. A summary table will include frequencies and percentages of treatment failure and a p-value for the treatment group difference.

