4.2.3 Secondary Efficacy Endpoints

Secondary efficacy endpoints are:

- No MEE assessed at the Day 4 and Day 28 visits by pneumatic otoscopy
- No bulging of the TM assessed at the Day 12 and Day 28 visits by pneumatic otoscopy
- Normal tympanogram (Type A) assessed at the Day 4, Day 12, and Day 28 visits by tympanometry
- Complete or near complete resolution of symptoms (AOM cure), defined as an AOM-SOS score ≤ 2, assessed at the Day 4 Visit, the Day 12 Visit and the Day 28 Visit.
- Change from baseline in the AOM-SOS score over the 10-day planned treatment period by parent/caregiver diary data
- At least a 50% reduction from baseline in the in-clinic AOM-SOS score, assessed at the Day 4, Day 12, and Day 28 visits
- AOM treatment failure (clinical failure) at the Day 12 Visit, with treatment failure defined as moderate to severe bulging of the TM, or mild bulging of TM with recent (less than 48 hours) onset of ear pain (otalgia), or mild bulging of the TM with intense erythema of the TM.
- AOM relapse defined as those with clinical success at the Day 12 visit and who return for an interim/sick visit before Day 17 and have AOM. Clinical success is defined as no moderate to severe bulging of the TM, and no mild bulging of the TM with recent (less than 48 hours) onset of ear pain (otalgia), and no mild bulging of the TM with intense erythema of the TM.
- AOM recurrence defined as clinical success at the Day 12 visit and return for an interim/sick visit from Day 17 through Day 28 and have AOM. Clinical success is defined as no moderate to severe bulging of the TM, and no mild bulging of the TM with recent (less than 48 hours) onset of ear pain (otalgia), and no mild bulging of the TM with intense erythema of the TM.

Confidential Page 11 of 35

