8.7 Visit Windows

Visit windows are based on Study Day. Observations will be assigned to an analysis window according to the tables below. Observations that cannot be assigned to an analysis window based on the tables below will be excluded from summaries and analyses (but will still be listed). For subjects not dosed, planned date of first dose will be used in Study Day calculations, if necessary.

For otoscopy and tympanogram parameters:

Nominal Visit	Target Study Day	Min Study Day Per Protocol	Max Study Day Per Protocol	Min Study Day for Analyses	Max Study Day for Analyses
Visit 1 (Day 1 Pre-Dose)	1 (pre-dose)	1	1 (pre-dose)	N/A	1 (pre-dose)
30 Minutes Post-Dose	1 (post-dose)	1 (post-dose)	1 (post-dose)	1 (post-dose)	1 (post-dose)
Visit 2 (Day 4)	4	4	6	4	6
Visit 3 (Day 12)	12	12	14	12	14
Visit 4 (Day 28)	28	26	30	26	30

N/A, not applicable

Confidential Page 15 of 35

Nominal Visit	Target Study Day	Min Study Day Per Protocol	Max Study Day Per Protocol	Min Study Day for Analyses	Max Study Day for Analyses
Visit 1 (Day 1)	1 (pre-dose)	1	1 (pre-dose)	N/A	1 (pre-dose)
Visit 2 (Day 4)	4	4	6	4	6
Visit 3 (Day 12)	12	12	14	12	14
Visit 4 (Day 28)	28	26	30	26	30

N/A, not applicable

For AOM-SOS score collected by diary:

Nominal Visit	Target Study Day	Min Study Day Per Protocol	Max Study Day Per Protocol	Min Study Day for Analyses	Max Study Day for Analyses
Visit 1 (Day 1)	1 (pre-dose)	1	1 (pre-dose)	N/A	1 (pre-dose)
Diary Day x, x=2-10	X	X	X	X	X

N/A, not applicable

If multiple valid, non-missing observations exist within a given window, the observation to be used will be:

- 1. the observation closest to the target study day of the nominal visit in question, or
- 2. the latest observation if the multiple observations are equidistant from the target study day of the nominal visit, or
- 3. the average (arithmetic or geometric, as appropriate) of the observations if the multiple observations have the same actual time point.

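### SAP 8.7 and 12.4 disagree on which days enter the 10-day diary AOM-SOS mean: as written, it either averages in the pre-dose baseline or cannot be calculated for any child

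*SAP*

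**What the plan says.** - **Outcome (SAP 12.4, Endpoints).** The analysed quantity is the "10-day mean AOM-SOS total score based on diary data, calculated for each subject as the mean total score over the 10-day treatment period".
- **Required count (SAP 12.4).** "If less than 10 days of AOM-SOS scores are available, 10-day mean score will not be calculated". In the other direction, "If more than 10 days of AOM-SOS scores are available, only the first 10 days will be used to calculate the mean". A missing Day 4 diary score may be replaced by the clinic score if that was taken on Study Day 4. No other clinic score is admitted by name.
- **Diary windows (SAP 8.7).** The diary table has two rows. One is Visit 1 (Day 1), whose latest analysis time is Day 1 pre-dose. The other is "Diary Day x, x=2-10", with each study day as its own window. Where a window holds several observations, one is selected or they are averaged, so each window yields one score.
- **Out-of-window data (SAP 8.7).** The rule reads in part: "Observations that cannot be assigned to an analysis window based on the tables below will be excluded from summaries and analyses (but will still be". Such scores appear in the data listings only.
- **Baseline (SAP 12.4).** Of the score obtained at the screening visit, the plan says: "This is the only baseline assessment of the AOM-SOS scale". SAP 8.6 defines baseline as the last value before the first dose.
- **Model (SAP 12.4, Summaries and Analyses).** A "general linear model (GLM) with baseline AOM-SOS total score included as a covariate". The table reports group means, SDs and a p-value.
- **Endpoint label (SAP 4.2.3, and likewise Protocol 9.4.1).** "Change from baseline in the AOM-SOS score over the 10-day planned treatment period by parent/caregiver diary data". SAP 16 does not list the move from a change score to a mean.

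**The concern.** The window table and the endpoint rule cannot both be applied without a choice that the SAP does not make. The windows give nine post-dose scores and one pre-dose score, while the rule demands ten. A programmer must either fill the tenth place with the pre-dose score, which is also the model covariate, or conclude that nobody qualifies. The rule for more than ten days can never be triggered, which also suggests that the two sections were written with different sets of days in mind.

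This affects a child with a perfect diary, so it is separate from the question of how many missing days to tolerate. If the pre-dose score goes in, the reported quantity is no longer a summary of symptoms under treatment. The AOM-SOS items ask about the preceding 12 hours (Protocol 8.2.4), so a pre-dose answer describes untreated time only and cannot respond to treatment. The means and the raw-point difference would then be read as post-dose results when one tenth of each is baseline.

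**Working it through.** The plan states no power or effect size for this endpoint. The one figure to reproduce is the count of ten.

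**1. Count the scores that SAP 8.7 can supply.**
- Day 1 pre-dose: 1
- Days 2 to 10: 10 − 2 + 1 = 9
- Day 1 post-dose: no window, excluded
- Day 11: no window, excluded
- Day 4 clinic score: replaces a missing Day 4 diary score and adds no day

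The maximum is 1 + 9 = 10 with the pre-dose score and 9 without it. More than ten is impossible.

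**2. Apply SAP 12.4 to each reading.**
- *Reading A, the pre-dose score counts.* A complete child has exactly ten scores, one of which is the baseline.
- *Reading B, the screening score is a clinic score and not diary data.* A complete child has nine scores. Nine is fewer than ten, so the mean is calculated for nobody.

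**3. Effect under Reading A.** Let B be the Day 1 pre-dose score, M the mean of Days 2 to 10, and Y the SAP mean.

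Y = (B + 9M)/10 = 0.1B + 0.9M

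B is a covariate in the GLM, so the term 0.1B is absorbed into its coefficient. The treatment coefficient, its SE and the residual SD for Y are therefore each exactly 0.9 times those for M. The t statistic, the p-value and the ratio of difference to residual SD do not change.

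**4. Numerical check.** One simulated trial of 137 children, with treatment, baseline and two stratifiers in the model (all simulated values are assumptions):

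| Outcome | Adjusted difference | SE | t |
|---|---|---|---|
| Mean of Days 2–10 | −1.590 | 0.299 | −5.308 |
| Ten scores including Day 1 pre-dose | −1.431 | 0.270 | −5.308 |

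The ratio is 0.900 for both estimate and SE. The unadjusted difference in Y also carries one tenth of any chance baseline imbalance: 0.9 × (−1.834) + 0.1 × (−0.876) = −1.738, which matches the simulated value.

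**5. Unadjusted group means under Reading A.** Each is shifted by Y − M = 0.1 × (B − M). The documents give no values for B or M beyond the entry requirement of a score of at least 5. Assuming a post-dose mean of 4.1:
- B = 8: shift 0.1 × 3.9 = 0.39
- B = 12: shift 0.1 × 7.9 = 0.79, so 4.1 is reported as 4.89
- B = 16: shift 0.1 × 11.9 = 1.19

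**6. Dependence on the reference period.** The factor 0.9 is relative to the Day 2–10 mean. Against other post-dose periods, the understatement of the expected difference depends on how the effect develops (assumed profiles):

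| Effect over time | vs Days 2–10 | vs post-dose Days 1–10 | vs Days 2–11 |
|---|---|---|---|
| Constant | 10.0% | 10.0% | 10.0% |
| Linear from zero on Day 1 | 10.0% | 0.0% | 18.2% |
| Proportional to day number | 10.0% | 1.8% | 16.9% |
| Early peak, then waning | 10.0% | 13.0% | 1.5% |

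**7. Change score.** Y − B = 0.9(M − B), so subtracting baseline from the ten-score mean leaves the same shrinkage. With B as covariate, Y and Y − B give the same treatment coefficient.

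**The case against.** The strongest reply is that SAP 12.4 itself points away from including the baseline. It speaks of diary data over the treatment period, distinguishes the diary from the clinic visits, and names only the Day 4 clinic score as a permitted substitute. The rule for more than ten days shows that its authors expected further diary days. Such entries are plausible. Protocol 4.1 has the diary completed on every treatment day, and the first dose is given on Day 1. If only one dose falls on Day 1, twenty doses given twice daily need 1 + 9 × 2 + 1, which reaches Day 11. The Day 1 pre-dose row also appears in the other SAP 8.7 tables, where it simply marks baseline.

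This stands as evidence of intent. It means that a reader who infers that the outcome definitely contains the baseline, and that the effect is definitely understated by 10%, goes further than the documents allow. It does not remove the conflict. As written, SAP 8.7 excludes a post-dose Day 1 or Day 11 entry, and keeping the screening score out leaves nine scores and no endpoint.

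A second reply is that the practical harm is small. That is largely right. The adjusted test is unaffected, and a future trial sized on the standardized effect from the same adjusted analysis would get the same sample size. A reader might infer that future trials would be mis-sized, and the documents do not support that beyond uses of the raw-point difference or the unadjusted means and SDs. The mismatch between change from baseline and mean is likewise a labelling matter for the treatment comparison.

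**Conclusion.** The point holds as a conflict between SAP 8.7 and SAP 12.4. Taken literally, the two sections give either a mean that includes the pre-dose baseline or an endpoint that cannot be calculated for anyone. The documents do not settle which.

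On the first reading, the adjusted raw-scale difference and its SE are 0.9 times those of the Day 2–10 mean. That factor is algebraic and needs no data assumption, but it depends on Days 2–10 being the reference. Under the four assumed profiles, the understatement is 0% to 13% against post-dose Days 1–10 and 1.5% to 18% against Days 2–11. The p-value, the power and the standardized effect of the adjusted analysis do not change. The size of the shift in the unadjusted means rests on assumed symptom levels.

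The consequence is modest: one secondary endpoint in a Phase 2a study, without multiplicity control. It is still worth correcting before analysis, because the present text forces an undocumented choice.

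**What to change.** 1. In SAP 12.4, define the outcome as the mean of post-dose diary scores only, and use the Day 1 pre-dose score solely as baseline and covariate.
2. Align the required count and the SAP 8.7 windows with that definition, in one of two ways: (a) Days 2 to 10, with the required count changed from ten to nine; or (b) ten days, with a post-dose Day 1 window or a Day 11 window added. Removing the baseline without changing either the count or the windows would leave every child without an outcome.
3. Delete or correct the rule for more than ten days, so that it can apply under the chosen windows.
4. Bring the label in SAP 4.2.3, the title of Table 14.2.4.1 and the list in SAP 16 into line with what is analysed.

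The cost is a few sentences in SAP 12.4 and 8.7, one table title and one added row in SAP 16. Option (a) needs no new data, and its downside is a mean that rests on nine days instead of ten. Option (b) keeps ten days but depends on the diary holding post-dose Day 1 or Day 11 entries, which should be confirmed on blinded data first.
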